### 5.9.2. Storage of Product

Study product supplies must be stored in compliance with the label requirements in a secure place, protected from sunlight, with limited or controlled access.

Document Name	207583 Protocol.docx		
Type	Version	Document Identifier	Effective Date
eldo_clinical_doc	3.0; Most-Recent; Effective; CURRENT	090032d580d40cd1	18-May-2017 10:48:45
Reason For Issue	Auto Issue		

## 6. STUDY ASSESSMENTS AND PROCEDURES

This section lists the procedures and parameters of each planned study assessment. The exact timing of each assessment is listed in the Schedule of Events section.

Adherence to the study design requirements, including all assessments and procedures are essential and required for study conduct.

### 6.1. Visit 1 – Subject Screening

#### 6.1.1. Informed Consent

The investigator, or designee, must obtain written (signed and dated by the subject) informed consent from each subject participating in this study after adequate explanation of the aims, methods, objectives, and potential hazards of the study.

The investigator, or designee, must also explain to the subjects that they are completely free to refuse to enter the study or to withdraw from it at any time. Appropriate forms for documenting a written consent will be provided by the investigator or by GSKCH. The investigator, or designee, should sign and date the consent form to confirm that the consent process was completed correctly. The subject, will be provided with a copy of their signed and dated consent form and any other written information which they should be instructed to retain.

If, during a subject's participation in the study, any new information becomes available that may affect the subject's willingness to participate in the study, each ongoing subject should receive a copy of this new information and be re-consented into the study. Subjects should be provided with a copy of the signed and dated amended consent form. The date of consent will be recorded on the CRF.

#### 6.1.2. Demographics and Baseline Characteristics

The following demographic parameters will be captured by the Investigator or designee and recorded on the CRF: year of birth, gender, race, Fitzpatrick skin type (see 6.1.5 for details) and Individual Typology Angle (see 6.1.4 for details).

#### 6.1.3. Medical History and Concomitant Medication

Medical history will be assessed as related to the inclusion/exclusion criteria by the Investigator or medically qualified designee. Details of any relevant medical or surgical history (within the last year), including allergies or drug sensitivity, will be

Document Name	207583 Protocol.docx		
Type	Version	Document Identifier	Effective Date
eldo_clinical_doc	3.0; Most-Recent; Effective; CURRENT	090032d580d40cd1	18-May-2017 10:48:45
Reason For Issue	Auto Issue		

recorded on the CRF. Any concomitant therapy taken in the 30 days prior to the Screening Visit and throughout the study will also be recorded.

#### 6.1.4. Individual Typology Angle (ITA°)

A tri-stimulus chromameter (Minolta CR 400, Langenhangen, Germany) which utilizes the L\*, a\*, b\* colour space and complies with International Commission on Illumination (CIE) recommendations will be used to measure the colour of each subject's skin (dorsum). Subjects will rest for 10 minutes in the prone position, with the skin area uncovered, to eliminate contact or stress-related redness and marks. During measurements, care will be taken to apply the cone aperture of the reflectance colorimeter sensing head so that it just makes contact with the skin, without any pressure, to avoid any skin "blanching" effect. Four measurements will be taken on the back of each subject, between the waist and shoulder line, and the individual L\*, and b\* values will be recorded as source data. The ITA° will be calculated as per Equation 1 and recorded on the CRF.

$$\text{ITA}^\circ = \left\{ \text{arc tangent} \left[ \frac{(L^* - 50)}{b^*} \right] \right\} \frac{180}{3.14159} \quad (\text{Equation 1})$$

\*arc tangent is expressed in radians.

The mean ITA° and historical data will be used to estimate the MEDu for each subject. The estimated MEDu will be recorded on the CRF.

#### 6.1.5. Fitzpatrick Skin Type Assessment

Fitzpatrick skin type assessment will be conducted by a trained, qualified technician or physician using the scale below.

Type	Description
I	Always burns easily: never tans
II	Always burns easily: tans minimally
III	Burns moderately: tans gradually
IV	Burns minimally: always tans well
V	Very rarely burns: tans profusely
VI	Never burns: deeply pigmented

The Fitzpatrick skin type will be recorded on the CRF.

Document Name	207583 Protocol.docx		
Type	Version	Document Identifier	Effective Date
elido_clinical_doc	3.0; Most-Recent; Effective; CURRENT	090032d580d40cd1	18-May-2017 10:48:45
Reason For Issue	Auto Issue		

### **6.1.6. Inclusion/Exclusion Criteria**

Inclusion/exclusion criteria will be assessed by the Investigator or designee and subject compliance with each criterion recorded on the CRF.

### **6.1.7. Subject Eligibility**

Subject eligibility to participate in the study will be assessed by the Investigator or medically qualified designee and recorded on the CRF.

## **6.2. Visit 2 – Provisional MED Irradiation (UV Exposure)**

Before starting the main test, a provisional MEDu will be determined for each subject in order to centre the UV dose ranges for the exposures of MEDu and MEDp.

### **6.2.1. Concomitant Medication**

Any concomitant therapy taken since the last visit and throughout the study will be recorded on the CRF by the Investigator or medically qualified designee.

### **6.2.2. Exclusion Criteria**

Subject compliance with exclusion criteria in Appendix 2 will be re-assessed by the Investigator or designee and subject compliance with each criterion recorded on the CRF.

### **6.2.3. Subject Eligibility**

Following the review of the exclusion criteria specified in 6.2.2, subject eligibility to continue in the study will be assessed by the Investigator or medically qualified designee and recorded on the CRF.

### **6.2.4. Continued Eligibility**

The Investigator or designee will ascertain whether there have been any deviations from the protocol since the last visit, whether the subject has adhered to the lifestyle restrictions since the last visit and whether, in their opinion, the subject is eligible to continue in the study and their decision will be recorded on the CRF.

### **6.2.5. Randomisation**

Subject randomisation will be conducted as per the process detailed in Section 5.8.1.

Document Name	207583 Protocol.docx		
Type	Version	Document Identifier	Effective Date
eldo_clinical_doc	3.0; Most-Recent; Effective; CURRENT	090032d580d40cd1	18-May-2017 10:48:45
Reason For Issue	Auto Issue		

## 6.2.6. Provisional Minimal Erythema Dose Irradiation

The specification of the solar simulator output is included in Appendix 3. A UV dose is the result of multiplying the UV source irradiance by the episode duration. In this study, a solar simulator with 6 light guides exposing all sub-sites for the same duration but with varied irradiance values will be used. Before UV exposure of each test site, irradiance values will be measured and recorded with a radiometer which has been calibrated with a spectroradiometric measurement of the solar simulator output.

A suitable warm-up time of at least 10 minutes will be allowed for the UV solar simulator to stabilize before starting exposures. This is to ensure a consistent irradiance over the whole exposure period. Subject exposure to UV radiation will be conducted in stable conditions, with the subject lying horizontally on their front (prone) and in a room with controlled temperature ( $22 \pm 4^\circ\text{C}$ ).

Test sites intended for UV exposure shall be free from blemishes and have an even colour tone. In this study, there will be a total of seven irradiated test sites. Three test sites will be demarcated below the scapula line and above the waist on the left side of the spine. The remaining four test sites will be demarcated below the scapula line and above the waist on the right side of the spine. The location of the test site for the provisional MEDu measurement will be randomised over the whole test group in order to reduce error arising from anatomical differences in skin.

Six exposure sub-sites centered on the estimated MEDu will be exposed with incremental UV doses using a geometric progression of 1.25. The dose of UV radiation administered will be chosen so that the 4th of the 6 sub-sites will be irradiated with the estimated MEDu. The estimated MEDu will be predicted based on the subject's mean ITA° value.

The minimum area of each exposure sub-site will be 0.5 cm^2. The minimum distance between borders of each exposure sub-site (spots) will be at least 0.8 cm. The distance between any exposure sub-site and any edge of the test site will be at least 1 cm.

Any extraneous exposure of the test sites to UV light (artificial or natural) will be avoided during this period and for a period of 24 hours after exposure. Any additional UV exposure to the test area will invalidate the whole test for the subject concerned.

Document Name	207583 Protocol.docx		
Type	Version	Document Identifier	Effective Date
elido_clinical_doc	3.0; Most-Recent; Effective; CURRENT	090032d580d40cd1	18-May-2017 10:48:45
Reason For Issue	Auto Issue		

## 6.2.7. Adverse Events

Adverse events will be assessed by the Investigator or designee and recorded on the CRF, as per the process detailed in Section 7. Localised erythema caused by exposure of the skin to UV radiation is expected and will not be reported as an adverse event.

## 6.3. Visit 3 – Provisional MEDu Determination

### 6.3.1. Concomitant Medication

Any concomitant therapy taken since the last visit and throughout the study will be recorded on the CRF by the Investigator or medically qualified designee.

### 6.3.2. Continued Eligibility

The Investigator or designee will ascertain whether there have been any deviations from the protocol since the last visit, whether the subject has adhered to the lifestyle restrictions since the last visit and whether, in their opinion, the subject is eligible to continue in the study and their decision will be documented on the CRF.

### 6.3.3. Visual Grading of Exposure Sub-Sites (Test Sites)

The MED is defined as the lowest dose of UV radiation that produces the first perceptible unambiguous erythema with defined borders appearing over most of the field of UV exposure, 16 to 24 hours after UV exposure.

The provisional MED will be assessed visually by a trained grader with the subject lying horizontally on their front and in a room with controlled temperature ( $22 \pm 4^{\circ}\text{C}$ ). The same grader will assess all subjects in the study. The grader's eyesight must have been checked for normal colour vision and acuity within the previous year. Visual assessment will be performed in a room with matt, neutral wall colours with sufficient and uniform illumination. As only one site will be exposed to UV radiation for the detection of the provisional MEDu, the grader will, necessarily, not be blinded at this point in the study.

The provisional MEDu of each subject will be recorded on the CRF with units of millijoules per square centimeter ( $\text{mJ/cm}^2$ ).

### 6.3.4. Adverse Events

Adverse events will be assessed by the Investigator or designee and recorded on the CRF, as per the process detailed in Section 7. Localised erythema caused by exposure of the skin to UV radiation is expected and will not be reported as an adverse event.

Document Name	207583 Protocol.docx		
Type	Version	Document Identifier	Effective Date
elido_clinical_doc	3.0; Most-Recent; Effective; CURRENT	090032d580d40cd1	18-May-2017 10:48:45
Reason For Issue	Auto Issue		

## 6.4. Visit 4 – Test Irradiation (UV Exposure)

### 6.4.1. Concomitant Medication

Any concomitant therapy taken since the last visit and throughout the study will be recorded on the CRF by the Investigator or medically qualified designee.

### 6.4.2. Continued Eligibility

The Investigator or designee will ascertain whether there have been any deviations from the protocol since the last visit, whether the subject has adhered to the lifestyle restrictions since the last visit and whether, in their opinion, the subject is eligible to continue in the study and their decision will be documented on the CRF.

### 6.4.3. Study Product Application to Randomly Assigned Test Sites on the Back

Test sites intended for UV exposure shall be free from blemishes and have an even colour tone. The total surface area of each test site shall be 40 cm^2. Test site demarcation and product application will be conducted in stable conditions with the subject lying horizontally on their front and in a room with controlled temperature (22 ± 4 °C).

CCI

| |

CCI

[figure not shown]

Document Name	207583 Protocol.docx		
Type	Version	Document Identifier	Effective Date
eldo_clinical_doc	3.0; Most-Recent; Effective; CURRENT	090032d580d40cd1	18-May-2017 10:48:45
Reason For Issue	Auto Issue		

CCI

CCI

#### **6.4.4. UV Exposure of Test Product Treated, Reference Sunscreen Formulation Treated and Unprotected Test Sites**

The specification of the solar simulator output is included in Appendix 3. A UV dose is the result of multiplying the UV source irradiance by the episode duration. In this study, a solar simulator with 6 light guides exposing all sub-sites for the same duration but with varied irradiance values will be used. Before UV exposure of each test site, irradiance values will be measured and recorded with a radiometer which has been calibrated with a spectroradiometric measurement of the solar simulator output.

A suitable warm-up time of at least 10 minutes will be allowed for the UV solar simulator to stabilize before starting exposures. This is to ensure a consistent irradiance over the whole exposure period. Subject exposure to UV radiation will be conducted with the subject lying horizontally on their front and in a room with controlled temperature ( $22 \pm 4$  °C).

The minimum area of each exposure sub-site will be  $0.5 \text{ cm}^2$ . The minimum distance between borders of each exposure sub-site (spots) will be at least 0.8 cm. The

Document Name	207583 Protocol.docx		
Type	Version	Document Identifier	Effective Date
elido_clinical_doc	3.0; Most-Recent; Effective; CURRENT	090032d580d40cd1	18-May-2017 10:48:45
Reason For Issue	Auto Issue		

distance between any exposure sub-site and any edge of the test site will be at least 1 cm.

Exposure of the test product and positive control treated sites to UV radiation will start 15 to 30 minutes after each product application has completed. Exposure of the unprotected site to UV radiation may happen at any point after demarcation of the test sites and after the 10 minutes required for the solar simulator to warm up. Exposure of the unprotected site, positive control and test product sites will be conducted sequentially, in any order, on same subject on the same day.

For the unprotected site, the range of UV doses administered shall be selected using the subject's provisional MEDu. Six exposure sub-sites centered on the provisional MEDu shall be exposed with incremental UV doses using a geometric progression of 1.12. The dose of UV radiation administered to subjects will be chosen such that the provisional MEDu will be irradiated on the 4th of the 6 sub-sites.

For the test product and reference formulation protected sites, the UV doses administered shall be selected using the subject's expected MEDp, which is the multiple of the expected SPF of the study product and the provisional MEDu for the subject. A minimum of 6 sub-sites centered on the expected MEDp shall be exposed with incremental UV doses using a geometric progression of 1.12. The dose of UV radiation administered to subjects will be chosen such that the expected MEDp will be irradiated on the 4th of the 6 sub-sites. After the UV exposure procedures are complete, reference and test product may be gently removed by wiping with a dry tissue.

Any extraneous exposure of the test sites to UV light (artificial or natural) will be avoided during this period and until visual evaluation is completed. Any additional UV exposure to the test area will invalidate the whole test for the subject concerned.

#### **6.4.5. Adverse Events**

Adverse events will be assessed by the Investigator or designee and recorded on the CRF, as per the process detailed in Section 7. Localised erythema caused by exposure of the skin to UV radiation is expected and will not be reported as an adverse event.

Document Name	207583 Protocol.docx		
Type	Version	Document Identifier	Effective Date
eldo_clinical_doc	3.0; Most-Recent; Effective; CURRENT	090032d580d40cd1	18-May-2017 10:48:45
Reason For Issue	Auto Issue		

## 6.5. Visit 5 – MEDp and MEDu Determination and SPF Calculation for Test and Reference Sunscreens

### 6.5.1. Concomitant Medication

Any concomitant therapy taken since the last visit and throughout the study will be recorded on the CRF by the Investigator or medically qualified designee.

### 6.5.2. Continued Eligibility

The Investigator or designee will ascertain whether there have been any deviations from the protocol since the last visit, whether the subject has adhered to the lifestyle restrictions since the last visit and whether, in their opinion, the subject is eligible to continue in the study and their decision will be recorded on the CRF.

### 6.5.3. Visual Grading of Exposure Sub-Sites to Determine MEDp and MEDu

The MED is defined as the lowest dose of UV radiation that produces the first perceptible unambiguous erythema with defined borders appearing over most of the field of UV exposure, 16 to 24 hours after UV exposure.

The MED determination will be assessed visually by a trained grader with the subject lying horizontally on their front in a room with controlled temperature ( $22 \pm 4$  °C). The same grader will assess all subjects in the study. The grader's eyesight must have been checked for normal colour vision and acuity within the previous year. Visual assessment will be performed in a room with matt, neutral wall colours with sufficient and uniform illumination. Erythema responses will be observed in a blind manner. The grader must not be the same person as the one who performed product application and exposure nor will the grader be aware of the test design (randomisation of test sites) for any subject.

The MEDu and MEDp values for each subject will be recorded on the CRF with units of  $\text{mJ/cm}^2$ .

### 6.5.4. Adverse Events

Adverse events will be assessed by the Investigator or designee and recorded on the CRF, as per the process detailed in Section 7. Localised erythema caused by exposure of the skin to UV radiation is expected and will not be reported as an adverse event.

Document Name	207583 Protocol.docx		
Type	Version	Document Identifier	Effective Date
elido_clinical_doc	3.0; Most-Recent; Effective; CURRENT	090032d580d40cd1	18-May-2017 10:48:45
Reason For Issue	Auto Issue		

### 6.5.5. Study Conclusion

Subjects will be evaluated to determine if they completed all study procedures or if they were discontinued from the study early. If the subject is discontinued at any point during the study, the primary reason for withdrawal shall be recorded on the Study Conclusion page of the CRF by selecting one of the options below.

1. Subject did not meet study criteria
2. Adverse Event
3. Lost to Follow Up
4. Protocol Violation
5. Withdrawal of Consent
6. Other

Document Name	207583 Protocol.docx		
Type	Version	Document Identifier	Effective Date
elido_clinical_doc	3.0; Most-Recent; Effective; CURRENT	090032d580d40cd1	18-May-2017 10:48:45
Reason For Issue	Auto Issue		

## 7. SAFETY ASSESSMENTS

### 7.1. Definitions of an Adverse Event and Serious Adverse Event

#### 7.1.1. Adverse Events

The investigator or site staff will be responsible for detecting, documenting and reporting events that meet the definition of an AE or SAE.

##### Adverse Event Definition:

1. An AE is any untoward medical occurrence in a patient or clinical investigation subject, temporally associated with the use of an investigational or washout product, whether or not considered related to the investigational or washout product.
2. NOTE: An AE can therefore be any unfavorable and unintended sign (including an abnormal laboratory finding), symptom, or disease (new or exacerbated) temporally associated with the use of an investigational or washout product.

##### Events meeting AE definition include:

1. Any abnormal laboratory test results (if applicable) or other safety assessments, including those that worsen from baseline, and felt to be clinically significant in the medical and scientific judgment of the investigator.
2. Exacerbation of a chronic or intermittent pre-existing condition including either an increase in frequency and/or intensity of the condition.
3. New condition(s) detected or diagnosed after study product administration even though it may have been present prior to the start of the study.
4. Signs, symptoms, or the clinical sequelae of a suspected interaction.
5. Signs, symptoms, or the clinical sequelae of a suspected overdose of either study product or a concomitant medication (overdose per se will not be reported as an AE/SAE).

##### Events NOT meeting definition of an AE include:

1. Any clinically significant abnormal laboratory findings (if applicable) or other abnormal safety assessments which are associated with the underlying disease, unless judged by the investigator to be more severe than expected for the subject's condition.
2. The disease/disorder/ condition being studied or expected progression, signs, or symptoms of the disease/disorder being studied, unless more severe than expected for the subject's condition.
3. Medical or surgical procedure (e.g., endoscopy, appendectomy): the condition that leads to the procedure is an AE.
4. Situations where an untoward medical occurrence did not occur (social and/or

Document Name	207583 Protocol.docx		
Type	Version	Document Identifier	Effective Date
eldo_clinical_doc	3.0; Most-Recent; Effective; CURRENT	090032d580d40cd1	18-May-2017 10:48:45
Reason For Issue	Auto Issue		

convenience admission to a hospital).

5. Anticipated day-to-day fluctuations of pre-existing disease(s) or condition(s) present or detected at the start of the study that do not worsen.
6. Localised erythema caused by exposure of the skin to UV radiation.

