test site will remain unprotected. The order of product application (test products, reference product and unprotected test site) will be randomised over the entire test group. Once the test products and positive control have been applied to the assigned test sites, the subject will undergo a second series of incremental UV exposures. For the unprotected site, the range of UV doses administered shall be selected using the subject's provisional MEDu. Six exposure sub-sites centered on the provisional MEDu shall be exposed with incremental UV doses using a geometric progression of 1.12. The dose of UV radiation administered to subjects will be chosen such that the provisional MEDu will be irradiated at the 4th of the 6 sub-sites. For the product protected sites, the UV doses administered shall be selected using the subject's expected MEDp, which is the multiple of the provisional MEDu for the subject and the expected SPF of either the test products (30) or reference sunscreen formulation (16). A minimum of 6 sub-sites centered on the expected MEDp shall be exposed with incremental UV doses using a geometric progression of 1.12. The dose of UV radiation administered to subjects will be chosen such that the expected MEDp will be irradiated at the 4th of the 6 sub-sites.

The target number of valid individual SPF (SPFi) results shall be 5. In order to achieve 5 valid results, a maximum of 3 individual invalid results may be excluded from the calculation of the mean SPF. Consequently, the actual number of test subjects randomised will fall between a minimum of 5 and a maximum of 8 subjects (i.e. a maximum of 5 valid results plus 3 rejected invalid results).

The study will include subjects of more than one Fitzpatrick phototype (I, II or III).

As this is a screening study, it will be permitted to adjust the expected SPF of each of the test products from subject to subject.

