### 9.2.2. Exclusion of Data from Analysis

Test data are deemed invalid and shall be rejected under the following circumstances:

1. The series of UV exposures on a subject fail to elicit an erythema response on any sub-site, 16-24 hours after exposure.
2. Erythema responses within an exposure series are randomly absent 16-24 hours after exposure.
3. All sub-sites in the exposure series show an erythema response 16-24 hours after exposure.

When one of the above criteria applies to the exposure of unprotected skin or reference sunscreen formulation exposure sites, then all data for all products on that subject are invalid and shall be rejected. When one of the above criteria applies to the exposure of a particular test product exposure site then data for that test product alone shall be invalid and rejected.

Any additional exposure of a test area to natural or artificial UV radiation will invalidate the whole test for that subject.

Major violations will be identified and any exclusion of subject data justified. Data deemed invalid due to protocol violations which are not related to the UV exposure procedures, such as illness, equipment failure, and subject drop out will not be included in analysis of efficacy and will not count towards the maximum of 3 invalid subject data. Data deemed invalid due to protocol violations related to the UV exposure procedures such as subject moving during irradiation will count towards the maximum of 3 invalid subject data.

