1.2 Study objectives

Objectives	Endpoints
Primary Objective	Primary Endpoint
To determine the Sun Protection Factor of the test products	Arithmetic mean of all valid individual sun protection factor (SPFi) values; where SPFi = Minimal Erythema Dose of product treated (MEDp) test sites in relation to unprotected (MEDu) test sites 16-24 hours after exposure to ultraviolet (UV) radiation.
Secondary Objectives	Secondary Endpoints
To determine the UVA Protection Factor of the test products	Arithmetic mean of all valid individual UVA protection factor (UVAPFi) values
To determine the critical wavelength of the test products	Wavelength for which the section under the integrated UV absorbance curve starting at 290 nm is equal to 90% of the integrated curve between 290 and 400 nm
To determine whether the test products provide broad spectrum sun protection	Ratio of the arithmetic mean SPF to the arithmetic mean UVAPF
To evaluate the general safety of the test product	Frequency and severity of Adverse Events.

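### Localised UV erythema is exempt from adverse event reporting with no severity limit, so redness alone that exceeds what the test intends has no defined route into the safety endpoint

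*Protocol*

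**What the plan says.** Protocol 7.1.1 lists events that do not meet the adverse event (AE) definition. Item 6 reads "Localised erythema caused by exposure of the skin to UV radiation" and carries no qualifier. Item 2, on the condition under study, applies only "unless more severe than expected for the subject's condition", and item 1 has a similar limit.

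Sections 6.2.7, 6.3.4, 6.4.5 and 6.5.4 repeat the exemption for Visits 2 to 5: "Localised erythema caused by exposure of the skin to UV radiation is expected and will not be reported as an adverse event". How much erythema is expected is not defined.

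Grading at Visits 3 and 5 (6.3.3, 6.5.3) determines the lowest dose giving a first perceptible, unambiguous erythema. No intensity scale is used. Section 9.2.2 foresees the case "All sub-sites in the exposure series show an erythema response 16-24 hours after exposure"; its stated consequence is that the data are rejected.

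The safety endpoint, in Protocol section 2 and SAP 1.2, is "Frequency and severity of Adverse Events". Intensity grading (7.3) and follow-up (7.5) attach to AEs.

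**The concern.** The test aims to produce a just-perceptible reddening. The most direct foreseeable harm is a stronger reddening than that, and the plan itself anticipates misjudged protection: it allows the expected SPF of a test product to change from subject to subject, and it has a rule for series in which every sub-site reddens.

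As written, redness of any strength that stays localised and is caused by the UV exposure is not an AE. It is then not graded for intensity, and the follow-up duty in 7.5 does not attach to it. Subjects are discharged at Visit 5, where grading takes place 16 to 24 hours after irradiation. A report of no skin AEs would look the same whether localised redness stayed at the intended level or went well past it. In a study whose safety endpoint includes severity, that is a gap in what the endpoint can show.

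**Working it through.** **Text comparison**

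- Items 1 and 2 of the list: exempt, up to a limit (more severe than expected).
- Item 6: exempt, no limit.
- Sections 6.2.7, 6.3.4, 6.4.5 and 6.5.4: exempt, no limit. They declare UV erythema as a class to be expected, rather than exempting only the expected amount.
- Grading at Visits 3 and 5: a threshold dose only.
- 9.2.2: an all-red series becomes invalid data, with no link to AE reporting.

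**Doses**

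The documents give no maximum dose in MED for a product that protects less than expected, so there is no figure of theirs to reproduce. The inputs are:

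- Expected SPF: 30 for test products, 16 for the P3 reference (Protocol 3.1, Overall Design).
- At least six sub-sites, with the expected protected MED (MEDp) at the fourth of six, exposed "with incremental UV doses using a geometric progression of 1.12" (6.4.4).
- Provisional unprotected MED (MEDu) read from a series with step 1.25 (6.2.6).
- True SPF: not given. The values below are assumptions.

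Dose at sub-site k, as a multiple of the expected MEDp, is 1.12^(k−4) for k = 1 to 6: 0.712, 0.797, 0.893, 1.000, 1.120, 1.254. At expected SPF 30 the range is 30 × 0.712 = 21.4 to 30 × 1.254 = 37.6 times the provisional MEDu.

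Dose reaching the skin, in MED, is (expected SPF ÷ true SPF) × 1.12^(k−4). The provisional MEDu is the lowest dose on its grid that reddens, so it can exceed the true MEDu by a factor of up to about 1.25. The last column applies that factor.

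| Assumed true SPF | Lowest sub-site, MED | Top sub-site, MED | Top, provisional MEDu one step high |
|---|---|---|---|
| 30 | 0.71 | 1.25 | 1.57 |
| 25 | 0.85 | 1.51 | 1.88 |
| 20 | 1.07 | 1.88 | 2.35 |
| 15 | 1.42 | 2.51 | 3.14 |
| 10 | 2.14 | 3.76 | 4.70 |

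Against the planned top dose of 1.25 MED, the ratio is 30 ÷ true SPF: 1.2 at SPF 25, 1.5 at SPF 20, 2 at SPF 15 and 3 at SPF 10.

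With an accurate provisional MEDu, all six sub-sites redden once the true SPF is at or below 30 × 0.712 = 21.4. Below that point no MEDp is determined. An all-red series at true SPF 20 (top dose 1.9 MED) and one at SPF 10 (3.8 MED) are then both recorded simply as invalid.

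For P3, a true SPF of 10 instead of 16 would give a top dose of 16 × 1.254 ÷ 10 = 2.0 MED.

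**The case against.** **Item 6 is narrow.** It exempts one sign from one cause. Blistering, pain, oedema and spread beyond the site are not named in it and remain AEs under the general definition in 7.1.1. Section 7.4 requires subjects to be asked about symptoms at each visit, and 7.2 collects AEs until 5 days after the last product application. Serious events are reportable in any case. This stands. A reader might infer that the endpoint cannot register an excessive burn at all; the documents do not support that. What remains uncovered is redness alone, which the 5-day window does not reach because it is not an AE.

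**Product irritation.** A reader might also infer that irritation on an irradiated site is excluded by definition. It is not: item 6 requires UV as the cause, and 7.3 requires a causality assessment. Telling the two apart may be difficult, but that is a diagnostic problem.

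**Size.** At least twice the planned top dose needs a true SPF of half the expected value or less, and how often that would occur is unknown. One could calculate that a product might over-expose four subjects (24 sub-sites) before its fourth invalid result stops it, but that assumes no correction after any of them, while the protocol permits the expected SPF to be adjusted. The mitigation is real but optional, and it cannot protect the first subject.

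**The analogy with items 1 and 2.** Those limits concern an underlying disease or condition, and these are healthy volunteers with a deliberately induced reaction. The word expected in section 6 arguably leaves room for judgement. That is fair, but the sentence labels the whole class as expected and item 6 has no such word, so two sites could read the text differently.

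**Traceability.** SAP Listing 16.2.6.1 gives the reason for exclusion by subject, site and treatment, so an all-red series can probably be identified there, though without its intensity.

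**Conclusion.** The point holds in a limited form. Five places in the protocol exempt localised UV erythema without a limit on severity or duration, while neighbouring items in the same list have a severity limit. Because grading captures only a threshold dose, stronger-than-intended redness on its own has no defined route into the frequency and severity of AEs.

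The dose figures show that this is possible under the plan, not that it is likely. They rest on assumed true SPFs and, outside the last column of the table, on an accurate provisional MEDu. A modest shortfall (SPF 20 to 25) gives a top dose of 1.5 to 1.9 MED; a large one (SPF 10 to 15) gives 2.5 to 3.8 MED. The gap in the wording exists whatever the true SPF is. Its effect is on what the safety report can show; the SPF estimates are not affected.

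**What to change.** Reconcile item 6 of the list in 7.1.1 and the statements in 6.2.7, 6.3.4, 6.4.5 and 6.5.4 with items 1 and 2. Add that UV erythema is not an AE unless the investigator judges it more severe, more extensive or longer lasting than expected for the test. The sponsor and investigator should decide and write down what counts as more than expected. Such cases would then enter intensity grading under 7.3 and follow-up under 7.5.

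The cost is one clause in five places and brief site training, with no added procedure. The downside is that a few more AEs may be recorded and that some investigator judgement is needed.

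Splitting the invalid count in SAP Table 14.2.1.1 into all sub-sites red, none red and random pattern is optional, since Listing 16.2.6.1 already carries the reason for exclusion and at most 8 subjects are planned.
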